6.7 Measles Virus shedding

Measles virus shedding will be analyzed in a subset of subjects randomized to treatment group A, B, C or D in the study center of AKH Vienna only at Visit 1 (Day 0), Visit 2 (Day 28) and Visit (Day 196). Besides the regular visits, subjects additionally will return to the study site on Day 7, 10, and 14 after the first injection.

Following tables/listing will be provided for the Final Analysis:

- The number of subjects participating in measles virus shedding (frequency statistics). •
- The number of sample performed by visit and treatment group (frequency statistics). •
- A data listing of measles virus shedding details (incl. date of separate informed consent and samples • obtained: urine/saliva/whole blood, sample results: urine/saliva).
- The number of subjects with positive shedding results (value ≥ 20) in urine by visit and treatment group • (frequency statistics).
- The number of subjects with positive shedding results (value ≥ 20) in saliva by visit and treatment group (frequency statistics).

Page 30 of 47

PHARMACOKINETICS / PHARMACODYNAMICS ANALYSIS 7.

Not applicable for this study.

Page 31 of 47

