#### 4.1.2 Secondary endpoints

- Immunogenicity on day 0, 28, 196 and 224; additionally, for group M1 and M2 on day -28 and 168 as confirmed by the presence of functional anti-chikungunya antibodies as determined by the plaque reduction neutralization test (PRNT50) and by ELISA.
- Measurement of anti-measles antibodies on day 0, 28, and 56; additionally, for group M1 and M2 on day -28 as determined by ELISA.
- Solicited local and systemic adverse events (AEs)
- Serious adverse events (SAEs)
- Rate of AEs during the 28 day post-vaccination period
- Safety laboratory parameters (hematology, serum chemistry, urinalysis)
- Shedding of live recombinant virus until day 196 (subset of subjects)
- Induction of a Chikungunya virus specific T cell responses (subset of subjects)
- Pre-existing anti-vector immunity:
  - Immunogenicity of Chikungunya vaccine in the presence of recently boosted measles immunity (measles booster groups M1 and M2).
  - Relation of post-vaccination anti-chikungunya plaque reduction neutralization titers (PRNT50) and baseline anti-measles ELISA titers (all treatment groups).

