## **6.2 Discussion of design**

The double-blind design will allow the most objective scoring of any adverse events. Block-randomization is considered to be necessary because of the limited group sizes.

Priorix® will be used as a control-vaccine because MV is the backbone of MV-CHIK. In case of unavailability or shortness of supplies also MMR-Vax-Pro or an equal measles vaccine may be used as control-vaccine.

Saline, serving as placebo control will be used to allow the assessment of absolute differences in signs and symptoms induced by MV-CHIK on an individual level and in order to maintain blinding of the sequence.

The sequence of vaccine injection on days 0 and 28 will allow assessment of the immunogenicity of two shots of the MV-CHIK vaccine 4 weeks apart. This sequence would be more realistic, if MV-CHIK will be used as a traveler vaccine.

The sequence of vaccine injection on days 28 and 196 will provide information on the immunogenicity of MV-CHIK after a single shot up to 196 days, which is also relevant for travelers. It will also allow testing of the immunogenicity of two shots of MV-CHIK (boosting vaccination after 24 weeks) in case the interval of 28 days between vaccinations is suboptimal for immunogenicity.

The shedding of infectious measles virus particles from a subset of immunized study subjects will be determined. Samples for shedding will only be collected from a subset of study subjects (of treatment groups A-D) that are enrolled at the study site in AKH Vienna. Body fluids including saliva, urine and whole blood will be collected at Visits 1, 2, and 5. In addition, the subjects will be asked to return to the study site on days 7, 10 and 14 after the first immunization for collection of saliva, urine and whole blood.

The induction of Chikungunya virus specific T cells is a critical step in the generation of a functional immune response. Only subjects (of all treatment groups) that are enrolled at study sites in Vienna will be included in a T cell investigation. For this purpose, peripheral blood monocyte cells (PBMC) from whole blood will be collected from the subjects. The frequency of Chikungunya virus specific T cells will be analyzed in vitro.

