#### 8.3.2 Measles virus shedding (AKH Vienna only)

Measles virus shedding will be analyzed in a subset of subjects randomized to treatment group A, B, C or D in the study center of AKH Vienna. Subjects will be asked if they are willing to participate in the virus shedding observation, which implies three additional site visits for sample collection. The participating subjects will sign a separate informed consent that describes the additional visits and procedures of sample collection. A minimum of 30 and a maximum of 50 subjects will be included in the shedding subset.

Besides the regular visits, these subjects additionally will return to the study site on day 7 ( $\pm 1$  day), 10 ( $\pm 1$  day), and 14 ( $\pm 1$  day) after the first injection. In addition, samples of saliva, urine and whole blood (2-3 mL) will be collected at Visit 1, 2, and 5.

The samples will be analyzed by quantitative PCR (by Envigo, Huntingdon, UK) to detect measles virus RNA. Any PCR positive sample will be further tested in an in vitro infectivity assay for the presence of infectious virus.

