Confidential and intellectual property of Assign DMB. No part of this document or its contents may be duplicated, referenced, published or otherwise disclosed in any form or by any means without prior written consent of Assign DMB.

			Immunogenicity Analysis	
3.1	х	х	Functional Antibodies Assessment (PRNT)	Subject number, Country, Treatment group,
			(Randomized subjects)	Visit, Functional antibody titer sample drawn,
				Date of sample, Time of sample, Titer [IU/ml]
3.2	Х	х	Functional Antibodies Assessment (ELISA)	Subject number, Country, Treatment group,
			(Randomized subjects)	Visit, Functional antibody titer sample drawn,
				Date of sample, Time of sample, Titer [IU/ml]
3.3	Х	х	Measles Antibodies Assessment (Randomized	Subject number, Country, Treatment group,
			subjects)	Visit, Measles antibody titer sample drawn,
				Date of sample, Time of sample, Titer [IU/mI],
				negative (no quantit. result available), Reason
				not drawn
3.4	Х	х	T-cell details (Randomized subjects)	Subject number, Country, Treatment group,
				Visit, Functional antibody titer sample drawn,
				Date of sample, Time of sample, Number of
				spots
3.5		х	Measles Virus shedding (Randomized subjects)	Subject number, Country, Treatment group,
				Measles virus shedding observation, Date of
				separate IC, Visit/Day, Date, Urine sample
				obtained, Saliva sample obtained, Whole Blood
				sample obtained, urine result, saliva result,
			Safety Analysis	
4.1		х	Extent of exposure (Randomized subjects)	Subject number, Treatment group, Date
				informed consent, Date of first vaccination,
				Date of last vaccination, Date of last attended
				visit, Treatment duration [days], Study duration
				[days]
4.2		х	Study medication details (Randomized subjects)	Subject number, Country, Treatment group,
				Vaccination been performed, Date/time,
				Nedication, Reason not vaccinated
1.0	Х	х	Adverse Events (Randomized Subjects)	Subject number, Treatment group, AE term,
4.3				Part 1: Country, Type (local solicited, systemic
				Solicited, unsolicited), MedDRA Preferred Term,
				Medically attended
1 1				Dert 2: Severity Serieue AF Coupelity Action
4.4				taken in general Action taken on the
				investigational product. Outcome
	v	v	Solicited local AFs (Bandomized subjects)	Subject number, Country, Treatment group, AF
	^	^		term
45				Part 1: Start date End date Medically
				attended Severity Serious AF
46				Part 2: Causality Action taken in general Action

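### The shedding endpoint is live recombinant virus, but SAP 6.7 reports only an undefined cut-off of 20 in urine and saliva, with no infectivity result and no whole-blood result

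*SAP*

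**What the plan says.** Protocol 4.1.2 lists the secondary endpoint as "Shedding of live recombinant virus until day 196 (subset of subjects"), and SAP 1.3.2 repeats it. Protocol 6.2 states the aim in the same sense: "The shedding of infectious measles virus particles from a subset of immunized study subjects will be determined".

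Protocol 8.3.2 sets out two laboratory steps. The first is quantitative PCR "to detect measles virus RNA". The second is conditional on the first: "Any PCR positive sample will be further tested in an in vitro infectivity assay for the presence of infectious virus". On sample types, protocol 6.2 says: "Body fluids including saliva, urine and whole blood will be collected at Visits 1, 2, and 5". Days 7, 10 and 14 after the first injection are added. On size, 8.3.2 says: "A minimum of 30 and a maximum of 50 subjects will be included in the shedding subset".

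SAP 6.7 plans, for the final analysis, a count of participants, a count of samples, a listing and two result tables. The first result table is "The number of subjects with positive shedding results (value ≥ 20) in urine by visit and treatment group"; the second is the same for saliva. These are Tables 3.1.25 and 3.1.26, repeated for the per-protocol population. For each subject, Listing 3.5 records whether urine, saliva and blood were obtained, but its result columns are urine and saliva only: "sample obtained, urine result, saliva result". SAP 2.17 declares no change from the protocol's planned analysis other than the timing of the preliminary analysis.

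**The concern.** PCR shows that measles virus RNA is present. Only the infectivity assay shows that virus in the sample is infectious. The endpoint is about live virus, so the second step is the one that answers it, and the SAP has no output for that step. Its positivity rule is a bare number without assay or unit, and one of the three sample types has no result at all.

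The vaccine is a live vector, and the box label in protocol 5.5 identifies a genetically modified organism. Exclusion criterion 25 and the condom requirement in 8.3.6 show that transmission to contacts was considered. Shedding is the planned measurement that bears most directly on that question. A report produced from these outputs could not say whether any subject shed live virus.

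**Working it through.** The plan states no sample size, power or target rate for shedding, so there is no figure to reproduce. The check is a comparison of texts and a count of samples.

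**Endpoint against outputs**

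| Element | Protocol | SAP 6.7, Tables 3.1.25–3.1.26, Listing 3.5 |
|---|---|---|
| Quantity | Live, infectious virus (4.1.2, 6.2) | Positive shedding, value at least 20 |
| Assay | PCR, then infectivity on PCR positives (8.3.2) | Not named |
| Unit and basis of cut-off | None given | None given |
| Urine, saliva | Six time points (Table 4) | Tabulated and listed |
| Whole blood | Six time points (Table 4) | Listed as obtained, no result |
| Infectivity result | Planned for every PCR positive | In no table or listing |

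**What the cut-off could mean.** Suppose 20 is a PCR quantity and L is the PCR positivity limit in the same unit.

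- If L = 20, a positive in the SAP is the same as a PCR positive. No sample sent for infectivity testing is counted as negative, but RNA without infectious virus counts as shedding.
- If L is below 20, samples from L up to 20 go to infectivity testing under 8.3.2 but count as negative in the SAP, even if infectious virus is found.
- If 20 is not a PCR quantity, the positivity rule is undefined.

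The SAP's other cut-offs do not settle this. In section 6, PRNT seroconversion is set at 10, the lowest value reported as a number. Chikungunya ELISA seroconversion is set at 16, against a lowest numeric value of 2.

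**Samples without a result.** From Table 4, 3 sample types × 6 time points = 18 per subject. Results are planned for 2 × 6 = 12. The remaining 6 of 18 are whole blood. For 30 subjects this is 30 × 6 = 180 of 540; for 50 subjects, 50 × 6 = 300 of 900.

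**How many of these follow a vaccine dose.** Groups B and D receive placebo on day 0 and first vaccine on day 28. The shedding sections do not say whether visit-day samples are drawn before or after injection. Assume an even split of the subset between the two schedules.

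- Drawn before injection: A and C have 5 (days 7, 10, 14, 28, 196), and B and D have 1 (day 196). The mean is (5 + 1)/2 = 3, giving 30 × 3 = 90 to 50 × 3 = 150.
- Drawn after injection: A and C have 6, and B and D have 2. The mean is 4, giving 120 to 200.

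With the 6:1 ratio of MV-CHIK to control vaccine, 6/7 of these follow MV-CHIK. In the first case that is 90 × 6/7 ≈ 77 to 150 × 6/7 ≈ 129.

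**Weight of one subject.** Over the whole subset, one subject is 1/50 = 2.0% to 1/30 = 3.3%. For the day 7 to 14 samples, only A and C recipients of MV-CHIK have had the vaccine: 30 × 1/2 × 6/7 ≈ 12.9 to 50 × 1/2 × 6/7 ≈ 21.4 subjects. One subject is then 1/21.4 ≈ 4.7% to 1/12.9 ≈ 7.8%.

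**The case against.** **The protocol at hand may not govern the shedding subset.** Shedding is sampled only at AKH Vienna, and the SAP rests on an Austrian and a German protocol. The supplied text matches the SAP's German schedule: it has Visit 7 on day 286, high-dose M1 and M2 groups, and a one-day window in the shedding footnote. A reader might infer that the SAP silently departs from the protocol that applied in Vienna. The documents do not show this, because the Austrian wording of 8.3.2 is not available. The objection limits what can be said about SAP 2.17. It does not touch the mismatch with the SAP's own endpoint in 1.3.2, and the Austrian flowchart in SAP 1.5.3 still lists blood, urine and saliva.

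**The cut-off may be harmless.** A reader might infer that infectious samples below 20 will be counted as negative. That follows only if the PCR positivity limit lies below 20, which the documents do not say. This part stands as an open question.

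**The listing may be fuller than it looks.** Its description in SAP 6.7 is not declared exhaustive, and the column list for Listing 3.5 ends in a comma, so lost text is possible. However, SAP 6.7 itself closes its list of results after urine and saliva, and the table list contains no blood or infectivity table. Results that are not tabulated are also not destroyed, and there may be no PCR positives at all.

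**Blood may show viraemia, not shedding.** That could justify omitting it. The protocol includes blood among the shedding samples, so the reason should be written down.

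**It is a small descriptive endpoint.** True: it has no hypothesis test and no bearing on the primary result. That limits its weight but does not remove the gap.

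**Conclusion.** The point holds. The SAP's shedding outputs do not measure the endpoint that the SAP names. No infectivity result is specified, the positivity rule has no stated assay, unit or basis, and whole blood has no result. The mismatch rests on the SAP's own text and needs no assumption.

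Its size is one third of scheduled samples per subject without a reported result: 180 to 300 blood samples in all, of which about 90 to 150 follow a vaccine dose if the subset splits evenly and visit samples precede injection. A reader who takes the full 180 to 300 as lost vaccine information would overstate the loss.

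That RNA detection would be reported as shedding depends on 20 being a PCR quantity. This is the likely reading, since PCR is the assay run on all samples, but it is not stated. Whether infectious samples could be missed cannot be decided from the documents. The change should be made before the final analysis. It does not affect the primary endpoint.

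**What to change.** In SAP 6.7:

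- State the assay, unit and basis of the cut-off of 20, and align it with the PCR positivity rule that triggers infectivity testing.
- Tabulate subjects with at least one infectivity-positive sample, by sample type, visit and treatment group, as the live-virus endpoint. Keep the analysis population already set for the shedding tables; nothing here calls for regrouping subjects by product received.
- Report PCR positivity separately and label it as RNA detection.
- Add whole-blood and infectivity results to the tables and to Listing 3.5, or declare and justify the omission of blood in SAP 2.17.
- Confirm the wording of 8.3.2 in the Austrian protocol, and record any difference in SAP 2.17.

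The cost is SAP wording, a few extra tables and some listing columns. The samples and both assays are already planned.

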8. SAFETY ANALYSIS

The mITT population will be used for the Preliminary Analysis, whereas the Safety population will be used for the Final Analysis. Analysis will be stratified by treatment group and overall. Safety analysis will be done except section 8.3 (Adverse event) for the Final Analysis only.

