### 13.2 Safety Analysis

Solicited AEs (reactogenicity): Solicited local and solicited systemic AEs will be summarized for the 7 day period, by AE grade (mild, moderate, severe), by group and by dose. Solicited AEs will not be coded into MedDRA or assessed for relatedness. The number and percentage of subjects with AEs will be presented. Subjects who reported data for a solicited event at any time point during the time period summarized would be included in the denominator for that event. Thus, denominators for each solicited event will not include subjects who were missing all data for that event, during the time period summarized. P-values for AE rates for MV-CHIK vs. Priorix® (or equal control-vaccine), for the same schedule, will be provided in summary tables (pairwise comparisons).

Unsolicited AEs: Separately, the number and percentage of subjects with unsolicited treatment emergent adverse events (TEAEs), medically-attended AEs (MAEs) and serious adverse events (SAEs) will be presented for each treatment group overall and by system organ class/preferred term, and by AE grade, and relatedness. All SAEs and MAEs are also included in TEAE tables. Arthritis AEs, AEs of special interest (AESI), will be included in the TEAE tables. For unsolicited AEs, all subjects entered into the study who receive at least one vaccination will be included in the safety analysis based on the product received (“as treated”), for the time period summarized. P-values for AE rates for MV-CHIK vs. Priorix®, for the same schedule, will be provided in summary tables (pairwise comparisons).

Unsolicited AEs and concomitant diseases will be coded using the MedDRA coding dictionary; concomitant medications will be coded using the WHO Drug Dictionary.

Solicited and unsolicited AEs (local and systemic), MAE, SAE and AESI (arthralgia) will be recorded up to Visit 6 (day 224).

Safety analyses will be performed by means of descriptive measures. Laboratory values will be assigned a grade. Changes in laboratory values and grades as well as vital signs from study entry to end of treatment/follow up will be analyzed descriptively.

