### 13.5 Analysis Populations

#### 13.5.1 Safety Population

All safety analyses for TEAEs will be based on the safety population, defined as subjects who entered into the study and received at least one vaccination. All analysis based on the Safety Population will be carried out using the actual treatment received. The denominators for reactogenicity rates are determined separately as discussed in section 0 (Safety Analysis).

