2.16 Analysis Populations

Three analysis populations will be used in this analysis:

• Modified Intent-to-Treat (mITT) Population

The exploratory immunogenicity analyses will be based on the modified ITT population. The modified Intent-to-treat (mITT) analysis population is defined to include all subjects randomized who receive at least one vaccination. Subjects will be analyzed according to the treatment group to which they are randomized to, rather than by the actual treatment they received.

• Safety Population (Final Analysis only)

All safety analyses will be based on the Safety population, which is defined to include all subjects who entered into the study and receive at least one vaccination. All analysis based on the Safety population will be carried out using the actual treatment received.

• Per-Protocol (PP) Population (Final Analysis only)

The Per-Protocol population is defined as mITT population excluding those subjects with at least one major protocol deviation. The PP population will exclude an enrolled subject if one of the following criteria is met:

- Immunosuppressive drugs: Use of corticosteroids (excluding topical preparations) or immunosuppressive drugs within 30 days prior to vaccination, or anticipated use during the trial.
- Subjects with any confirmed immunosuppressive or immunodeficient condition, including human immunodeficiency virus (HIV), hepatitis A, B or C infection or a family history of congenital or hereditary immunodeficiency
- Subjects who received the wrong or no study medication
- Subjects with other major protocol deviations

SAP (MV-CHIK-202, FINAL 3.0, 09-May-2018) Based on: STAT03_A Statistical Analysis Plan Version 5.0, Effective Date 16-Dec-2016 Confidential and intellectual property of Assign DMB. No part of this document of Page 20 of 47

These criteria for potential protocol violation were identified at the time of planning the study. However, during the course of the trial unforeseen events may occur or new scientific knowledge may become available, therefore final decisions on whether any protocol violation could impact immune response and thus lead to exclusion from the PP population will be made by the sponsor on a case by case basis in a data review meeting. Sample testing issues may also lead to exclusion from the PP population for particular time points.

Changes in the Conduct of the Study or Planned Analysis 2.17

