10.3 List of Figures

No	IA	FA	Legend
			Safety Evaluation
4.1	Х	Х	Bar chart for number of subjects with local solicited adverse event by symptom and severity
			MV-CHIK vs. control (safety population)
4.2	Х	Х	Bar chart for number of subjects with systemic solicited adverse event by symptom and
			severity MV-CHIK vs. control (safety population)
4.3	Х	Х	Bar chart for number of subjects with unsolicited adverse event by symptom and severity for
			the five most frequent unsolicited adverse events MV-CHIK vs. control (safety population)

Page 47 of 47

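### The preliminary adverse event tables are set to mITT as randomised, against the protocol's as-treated rule and the label on the preliminary figures; results change only if someone was misdosed before the cut-off

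*SAP*

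**What the plan says.** **Protocol.** Section 13.5.1 sets the population: "All safety analyses for TEAEs will be based on the safety population". It also sets the assignment rule: "All analysis based on the Safety Population will be carried out using the actual treatment received". Section 13.2 repeats the rule for unsolicited events: "all subjects entered into the study who receive at least one vaccination will be included in the safety analysis based on the product received". Section 13 says that the preliminary analysis includes safety data, and nothing there exempts it from these rules.

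**SAP, text.** Section 8 splits the populations by analysis: "The mITT population will be used for the Preliminary Analysis, whereas the Safety population will be used for the Final Analysis". Section 2.16 defines mITT by membership, "analysis population is defined to include all subjects randomized who receive at least one vaccination", and by assignment: "Subjects will be analyzed according to the treatment group to which they are randomized to, rather than by the actual treatment they received". The same section lists the as-treated population under the label "Safety Population (Final Analysis only", so it is not provided for at the preliminary analysis.

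**SAP, outputs.** In section 10.1, adverse event Tables 4.2 to 4.11 are marked for both analyses and carry a placeholder population, which is set to Safety at the final analysis. In section 10.3, Figures 4.1 to 4.3 are also marked for both analyses, but each has a single legend ending "MV-CHIK vs. control (safety population".

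**SAP, declared changes.** Section 2.17 says that no change from the protocol's planned analysis is intended. The only exception it notes is the earlier date of the preliminary analysis.

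**The concern.** The SAP departs from the protocol on how adverse events are attributed at the preliminary analysis, and it does so without saying so. Read literally, one preliminary report would hold tables by randomised group and figures by product received.

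For safety, attribution by product received is the usual choice because a reaction belongs to what was injected. Suppose a subject randomised to control vaccine is given MV-CHIK by mistake and reacts. The preliminary tables would count the reaction under control, and so would the unadjusted Fisher tests of SAP 2.7.3. The protocol's rule would count it under MV-CHIK.

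Both documents foresee dosing errors: receipt of wrong study medication is a ground for exclusion from the per-protocol population (Protocol 13.5.3, SAP 2.16). The planned preliminary outputs would not reveal one. The study medication listing (4.2) and the protocol deviation listing (1.3) are marked for the final analysis only, and SAP 2.14 collects deviations only for that analysis. SAP 2.2.1 says that the preliminary analysis was re-scheduled to help further vaccine development, so readers outside the trial team may rely on it.

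**Working it through.** The plan gives no figure on this point to reproduce. The check compares the texts and then sizes the possible effect.

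**1. Rules side by side**

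| Output | Population | Assignment | Source |
|---|---|---|---|
| TEAEs and unsolicited AEs, any analysis | Safety | As treated | Protocol 13.5.1, 13.2 |
| Tables 4.2–4.11, preliminary | mITT | As randomised | SAP 8, 2.16 |
| Figures 4.1–4.3, preliminary | Safety (legend) | As treated, if the legend is followed | SAP 10.3 |
| Tables and figures, final | Safety | As treated | SAP 8, 2.16, 10.1, 10.3 |

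The second row conflicts with the first and, on the legend, with the third. Both populations require at least one vaccination. They could differ in membership only for someone vaccinated without being randomised. The practical difference is therefore the column in which a subject is counted.

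**2. Inputs for the size**

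Protocol 6.3 plans 60 MV-CHIK and 10 control subjects in each of groups A to D. SAP 2.3 forms CV1 from the controls of A and C, and CV2 from those of B and D. So CV1 = 20, CV2 = 20 and all controls = 40. The documents give no count of dosing errors. One is assumed here: a subject randomised to control who received MV-CHIK and had the event.

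**3. Shift in the control rate**, with k events among the other control subjects

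- CV1 or CV2: (k+1)/20 − k/19 = (19 − k)/380. At k = 0 this is 5.0 points; at k = 10 it is 9/380 = 2.4 points.
- All controls: (k+1)/40 − k/39 = (39 − k)/1560. At k = 0 this is 2.5 points; at k = 20 it is 19/1560 = 1.2 points.

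The values at k = 0 are the maxima.

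**4. Direction**

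With e events as treated in a 61-subject MV-CHIK column, assignment as randomised lowers that rate by e/61 − (e − 1)/60 = (61 − e)/3660. The control rate rises and the MV-CHIK rate falls, so an excess on MV-CHIK shrinks. If the misdosed subject had no event, the direction reverses: control changes from k/19 to k/20 and MV-CHIK from e/61 to e/60. For events that the vaccine tends to cause, the first case is the likelier one, so the shift is usually, but not always, towards no difference.

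**5. Sensitivity of a Fisher test** (group A against CV1, event counts assumed)

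| As treated | p | As randomised | p |
|---|---|---|---|
| 13/61 vs 0/19 | 0.031 | 12/60 vs 1/20 | 0.17 |
| 8/61 vs 0/19 | 0.19 | 7/60 vs 1/20 | 0.67 |

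In the first row the difference falls from 21.3 − 0 = 21.3 points to 20.0 − 5.0 = 15.0 points. Both rows use zero events in the other controls, which is the most sensitive case. They show what one subject can do and are not a forecast. With no misdosed subject, the two assignments give identical results.

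**The case against.** The strongest reply is that nothing need follow from the mismatch.

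- **No misdosing is reported, and the protocol guards against it.** Unblinded authorised staff prepare the products (5.4), syringes carry subject ID and visit number (5.5), used containers are kept until the unblinded monitor has checked them (5.7), and an administration log is verified (5.8). This stands. The effect is conditional, and the safeguards lower its probability without excluding it.
- **The final analysis is already as treated, and preliminary results do not alter study design or treatment** (Protocol 13, SAP 2.2.1). This stands. Only the preliminary read-out is exposed.
- **The figure legend may be a slip.** One legend serves both analyses, and SAP 8 and 2.16 point to mITT for the preliminary one. This is plausible. A reader might infer that the preliminary figures will certainly be as treated; the documents do not settle that. The conflict between the tables and the protocol remains either way.
- **The protocol's wording has limited scope.** Section 13.5.1 names TEAEs and the product-received sentence in 13.2 covers unsolicited events, while solicited events have their own denominator rule. The contradiction is therefore direct for Tables 4.3 to 4.11 and weaker for the solicited Table 4.2. The SAP itself treats all ten tables alike at the final analysis, so including 4.2 in the fix is consistent.
- **Timing.** This SAP is Final 3.0, dated 09-May-2018, and the preliminary analysis was scheduled for August 2017. Rewording may come too late to govern it, so the fix needs a retrospective part. The moved date also means that the preliminary denominators may be below the planned ones; the maxima above hold only at planned sizes.

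**Conclusion.** The inconsistency is established by the texts. The preliminary adverse event tables follow randomised group, the protocol requires the product received for TEAEs and unsolicited events, the preliminary figures are labelled with a population that the SAP reserves for the final analysis, and the departure is not declared.

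Its effect on results is conditional. It needs a subject who received the wrong product before the preliminary cut-off. For one misdosed control subject with an event, the control rate moves by at most 5 points in CV1 or CV2 and at most 2.5 points in all controls, at planned sizes. The shift roughly halves when about half of the other controls also have the event.

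A reader might infer that the preliminary safety contrast is biased, or that 5 points is the expected error. The documents support neither: they report no misdosing, and 5 points is a ceiling. Nor do they support any doubt about the final safety analysis, which is as treated. This is a correction worth making because it is cheap and because the preliminary outputs would not show an error if there were one.

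**What to change.** In SAP 2.16, remove the restriction of the Safety population to the final analysis. In SAP 8 and for Tables 4.2 to 4.11, specify the Safety population by product received at both analyses. Tables, figures and protocol then agree, and the legends of Figures 4.1 to 4.3 can stay as they are.

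If the preliminary report has already been issued, declare the mITT choice in SAP 2.17 as a departure from the protocol and check dosing records up to the preliminary cut-off. If nobody was misdosed, a sentence saying so closes the point. If anyone was, correct the affected tables and tests.

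The cost is SAP wording and a check of actual treatment at the preliminary cut-off. The as-treated tables are needed for the final analysis in any case, but the check is a real task because deviations and study medication details are not planned preliminary outputs.
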